Interested parties will be provided with a telephone number and electronic mailing address to contact study personnel for more information regarding the study. A verbal consent form followed by a brief telephone screen will be used to assess initial eligibility; if research participants meet inclusion criteria based on the screening, the research participant will be scheduled for an initial clinical assessment with a trained assessor. If the research participant reports use of compensatory behaviors 3 or more times per week (i.e., purging and/or using laxatives), or endorses medical symptoms related to their eating disorder on the phone screen, we will ask the research participant to receive medical clearance from his or her PCP prior to enrollment in the study to ensure the research participant is safe to receive outpatient treatment. If the research participant refuses to obtain medical clearance or receive medical monitoring as requested by the study, they will be informed that they will not be eligible for participation in the study. Materials for their PCP will be mailed or emailed to research participants so they can obtain medical clearance for participation prior to their initial clinical assessment visit. Written or electronic informed consent will be obtained at the clinical assessment. The consent form will contain all pertinent details of the study procedure. Research participants will be clearly informed of the voluntary and confidential nature of their participation, and their right to terminate treatment at any time without penalty. After

PROTOCOL TITLE: Using factorial design to examine efficacies of technology-based augmentations for improving treatment adherence and skills utilization in a self-help CBT program for binge eating.

Protocol Version Date: April 19, 2022

research participants read the consent form, the program staff will paraphrase each segment of the consent form and will answer any questions. If the research participant agrees to participate, the consent form will be signed and witnessed. If the research participant chooses not to participate, they are given the option to be added to our study database to be contacted for other studies they might be eligible for at the WELL Center in the future. They will also be offered referral lists for other resources if they are interested. If they choose not to be entered into the database, all their information will be destroyed upon the completion of the study.

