- ***Eating Disorder Diagnosis***. This measure will be used to determine a research participant's eating disorder diagnosis based on the presence, frequency, and duration of pathological behavioral symptoms a research participant endorses at the assessment point.
- ***Feedback Questionnaire***. This measure will be used to assess research participant's overall enjoyment and perceptions of the treatment and assessments. The measure

PROTOCOL TITLE: Using factorial design to examine efficacies of technology-based augmentations for improving treatment adherence and skills utilization in a self-help CBT program for binge eating.

Protocol Version Date: April 19, 2022

will be conducted as an interview at mid-treatment (after 6 weeks of treatment) and post-treatment (after 12 weeks of treatment).

Self Report Measures

- ***Demographics Questionnaire (DQ)***. The Demographics Questionnaire will assess information such as age, sex, gender, sexual orientation, ethnicity, and SES.
- ***Dieting and Weight History Questionnaire (DWHQ)***. The DWHQ evaluates weight suppression, weight history, current and previous dieting history.
- ***Beck Depression Inventory-II (BDI-II)***. The BDI-II measures depression symptomatology over the past 2 weeks.
- ***Quality of Life Inventory (QOLI)***. The Quality-of-Life Questionnaire assesses quality of life across several life domains
- ***Short Positive and Negative Affect Scale (PANAS)***. The PANAS assesses positive and negative affect over a specified period of time.

Other measures

- ***Treatment adherence*** will be indicated by number of completed modules within 12 weeks of treatment, number of pages visited, number of worksheets completed, and goals setting each week using the app and self-monitoring compliance (i.e., number of days when self-monitoring was completed).

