not in use. Baseline and follow-up measures will be linked by the unique identifiers employed (which will be stored in the password protected excel database, only accessible when connected to Drexel's VPN and Drexel's secure REDCap system). Research participant consent forms will stipulate the research activities and treatment services they can anticipate and the protections they will receive. Study findings will make use of aggregate data only and no publication or presentation will involve any use of individual or personalized information. All physical copies of medical information collected as part of the medical clearance process will be kept confidential by project staff and stored in locked cabinets in locked offices at Drexel University. All electronic copies of medical information collected as part of the medical clearance process will be received from research participants through Drexel's secure Outlook system and the information will be password protected and stored on a secure network.

12) Data Management

Data collection, storage, and quality control. Data for those who fail screenings and do not meet inclusion criteria will be destroyed or, with consent from the participant, participants may be screened for another study or added to the WELL Center database to be contacted for future studies.

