All data will all be de-identified and code numbers will be used to integrate the various data collected from each subject. The pre and post study self-report questionnaires will be completed on the research participant's computer using a secure survey collection website (Drexel's REDCap system). Unidentifiable data will be downloaded and entered into SPSS. Data files will not contain personal health information. Name and contact information will be stored in a separate password-protected Excel database, only accessible when connected to Drexel's VPN and Drexel's secure REDCap system, to enable the researchers in facilitating remuneration and future contact. Names will not be linked to data. All electronic files will be stored on a Drexel-owned computer in an encrypted password protected directory that can only be accessed by specific, trained users. Data is de-identified and will not contain PHI including information pertaining to mental health diagnosis or treatment, and is stored on an encrypted backend server(a unique subject identification number will be used in place of participants names to identify input from the app). Our server utilizes industry-standard encryption techniques (e.g., secure sockets layer; SSL) to facilitate secure data transfer from subject device to study repository). For data analysis purpose, data from our server will be downloaded to Drexel-owned computers. All data will be stored on research lab computers with encrypted storage in password-protected files. All paper surveys (if any) will be labeled with non-identifiable information and stored in a locked filing cabinet in a limited access, password protected office at the Drexel University Center for Weight, Eating, and Lifestyle Science (WELL Center). All data will be erased or shredded in the standard 3 years after publication of results. The data collected by the smartphone application will not be shared with other smart devices, third parties or specified organizations. All the data you entered in the app will be saved on an encrypted back-end server, which will be linked to the unique research participant identifier assigned to you. No personal health information will be linked to this data collected from the smartphone application and

PROTOCOL TITLE: Using factorial design to examine efficacies of technology-based augmentations for improving treatment adherence and skills utilization in a self-help CBT program for binge eating.

Protocol Version Date: April 19, 2022

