Research participants will be withdrawn from the study if they no longer meet the study criteria and/or they experience any acute life-threatening incident (precipitous drop in weight, change in electrolyte balance, etc.), hospitalization, suicidal or homicidal ideation, or serious self-harm behavior, failure to comply with study procedures. Condition of pregnancy will be assessed during the baseline, mid-treatment, post-treatment, and 3 month follow-up. If the research participant finds out that they are pregnant or plan on becoming pregnant within the next year during their time in the study, they must notify the project coordinator immediately. They will no longer meet study criteria and will be withdrawn from the study immediately. If termination is found necessary, the research participant will be contacted by the project coordinator immediately and the necessary precautions will be taken to ensure safety or medical attention as appropriate. The research participant will then be provided with referrals to other programs or studies if applicable and the data will be destroyed/banned from use. If, at any time, the treating physician determines that the health of the research participant precludes continuation of outpatient treatment, a meeting will be scheduled with the treating physician, research participant, and study staff to assist in locating referrals for appropriate levels of care. If a higher level of care is sought, research participants will be removed from the trial. Research participants are given the option to be added to our study database to be contacted for other studies they

PROTOCOL TITLE: Using factorial design to examine efficacies of technology-based augmentations for improving treatment adherence and skills utilization in a self-help CBT program for binge eating.

Protocol Version Date: April 19, 2022

might be eligible for at the WELL Center in the future. If they choose not to be entered into the database, all their information will be destroyed.

15) Risk to Subjects

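### Protocol section 14 destroys or bars from use the data of terminated participants, with no exemption for those already randomised

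*Protocol*

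**What the plan says.** **Withdrawal rule.** Protocol section 14 opens: "Research participants will be withdrawn from the study if they no longer meet the study criteria". It adds acute life-threatening incidents and then "hospitalization, suicidal or homicidal ideation, or serious self-harm behavior, failure to comply with study procedures". Pregnancy, or a plan to become pregnant within a year, also leads to immediate withdrawal. Pregnancy is checked at baseline, mid-treatment, post-treatment and 3-month follow-up.

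**Data rule.** If termination is found necessary, the participant is contacted and given referrals, and "the data will be destroyed/banned from use". The section ends with an offer to join a database for contact about other studies: "If they choose not to be entered into the database, all their information will be destroyed".

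**Other data rules.**
- Section 10 (Consent procedures), for people who decline to take part: "If they choose not to be entered into the database, all their information will be destroyed upon the completion of the study".
- Section 12 (Data Management), for screen failures: "Data for those who fail screenings and do not meet inclusion criteria will be destroyed".
- Section 12, in general: "All data will be erased or shredded in the standard 3 years after publication of results".
- Section 24 (Recruitment Methods): people who stop treatment are encouraged to keep attending assessments.

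**Suicidal ideation.** Section 10 grades acute risk. High risk is removed from the study; intermediate and low risk may continue.

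**Missing data.** The SAP (Statistical Design and Power) plans likelihood methods and multiple imputation, with sensitivity analyses if missingness depends on the missing outcome.

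**The concern.** A randomised comparison is protected by analysing everyone who was randomised. A rule that deletes or bars a participant's whole record because of something that happened after randomisation removes that protection. The triggers here are not neutral: hospitalisation, suicidal ideation, self-harm and acute medical deterioration can all reflect how the participant is doing. If such people vanish from the analysis, each factor is compared among those who were not terminated, and the comparison can be biased.

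The planned missing-data methods do not help. Under likelihood or imputation, a participant who drops out still contributes the outcomes observed before dropout, and those outcomes inform what was missed. Once they are gone, the participant either contributes nothing or is imputed as though similar to the rest of the arm. A sensitivity analysis could assign assumed values to an empty record, but it could not recover what had been measured. Aim 4 is affected too, because it needs the change in adherence and skills use from baseline to mid-treatment.

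**Working it through.** This is settled mainly by the text. The arithmetic shows only what is lost per person.

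**1. Does the rule reach randomised participants?** Section 10 (Screening) places randomisation after the baseline assessment. Section 14 checks pregnancy at three later visits and withdraws at once. So the rule reaches randomised participants, including one who has finished all 12 weeks and reports a pregnancy at the 3-month visit.

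**2. Does anything override it?**
- The Consent procedures sentence covers people who never joined.
- The first section 12 sentence covers screen failures.
- The 3-year erasure rule is general and does not mention withdrawals.
- Section 24 concerns people who stop treatment. It does not mention those the study terminates, or their data.
- The SAP does not address destroyed or barred records.

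The resemblance between section 14 and the pre-enrolment sentences suggests carried-over text, but no section limits it to pre-enrolment. Barred from use may mean stored but not analysed; for the analysis the effect is the same.

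**3. Loss per person.** Enrolment is 76, so each terminated participant is 1/76 = 1.3%. There are four assessments (baseline, mid-treatment, post-treatment, 3-month). Mid-treatment falls after 6 of 12 weeks. Termination just after it means up to 2/4 assessments and 6/12 weeks of app records already collected. Usable under section 14 as written: none. Usable under a retention rule: all.

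**4. Against the plan's attrition allowance (illustration only).** The SAP Power Analysis gives N = 64 for binge eating frequency, with d = 0.78, four assessments, alpha 0.05, 80% power and variance ratio 1. Assume a two-sided test and equally spaced times 0, 1, 2, 3.

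- V = 1/Σ(t − t̄)² = 1/5 = 0.2
- Noncentrality = N·d²/[4(1 + V)] = 64 × 0.6084/4.8 = 8.11
- Power from the noncentral F(1, 62) = 80.1%, which reproduces the stated 64
- 64/(1 − 0.15) = 75.3, rounded up to 76, which reproduces the stated enrolment

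The documents give no termination rate. Over an assumed range of participants lost completely:

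| Lost of 76 | Remaining | Power |
|---|---|---|
| 0 | 76 | 86.5% |
| 4 (5.3%) | 72 | 84.6% |
| 8 (10.5%) | 68 | 82.5% |
| 12 (15.8%) | 64 | 80.1% |
| 15 (19.7%) | 61 | 78.1% |
| 19 (25.0%) | 57 | 75.2% |

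Twelve complete losses from all causes use up the allowance (76 − 64 = 12). These figures do not show how many will be lost, and they say nothing about bias, which is the main issue.

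**5. The ideation trigger.** For low or intermediate acute suicide risk, section 14 says withdraw and section 10 says continue. No section says which governs. Section 10 does not grade homicidal ideation, so there is no such conflict there.

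**The case against.** The best defence is that the plan, read as a whole, intends to keep people in. Section 24 keeps those who stop treatment in assessments, section 19-style removal wording elsewhere is silent on data, and the section 14 data sentence looks like pre-enrolment text. That is a fair guess at intent, but it does not exempt the randomised participants whom section 14 plainly reaches.

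Several other objections stand, and they limit the point:

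- **Low app use.** A reader might infer that non-compliance removals would delete low values of the Aim 1 adherence outcome, which counts "number of completed modules within 12 weeks of treatment, number of pages visited, number of worksheets completed" among its indicators. The compliance trigger is undefined, so this is a possible reading. The documents point the other way: section 10 makes missed tracking an occasion for a JITAI prompt, coaches respond to the same data, and section 24 keeps treatment discontinuers in assessments.
- **Exclusion 3.** A reader might infer that any suicidal ideation ends eligibility, because section 5 names suicidality. That criterion requires severe psychopathology that limits ability to engage, and low-risk ideation need not meet it.
- **The database sentence.** It follows an offer about contact for other studies and can be read as covering registry information only. It is not clearly a second rule on trial data, but its breadth warrants clarification.
- **Other removal statements.** The passages on removal in sections 10 and 15 do not mention data, so they need no rewriting.
- **Ideation.** Section 14 ties its later steps to termination being found necessary, and the section 10 grading could decide that. Its opening words still require withdrawal, so a small conflict remains. It is chiefly a clinical-safety matter.

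**Conclusion.** The point holds: section 14 as written excludes the observed data of randomised participants because of post-randomisation, partly outcome-related events, and no other section or planned method undoes this. It should be corrected.

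Its size is unknown. The documents give no termination rate, no split by arm and no link between termination and outcome, so neither the number affected nor the bias can be computed. A reader might infer a definite bias or loss of power; neither is shown. The firm statement is the loss per person in step 3.

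The conclusion assumes that section 14 would be applied literally and that the consent form, which is not in our copy, does not itself settle the matter. The ideation conflict is real but minor.

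**What to change.** **Main change, section 14.** Replace the data sentence with a rule that:
- data collected before withdrawal are retained and analysed as randomised, subject to any deletion promise in the consent form;
- remaining assessments are offered where clinically safe, in line with section 24.

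State that the destruction sentence for people who decline the contact database covers contact-registry information only, not randomised participants' trial data. Because sections 10 and 13 bar concurrent psychotherapy as a possible confounder, the SAP should say how assessments made after referral to outside care are analysed.

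**Minor change.** Cross-refer the suicidal-ideation trigger in section 14 to the graded assessment in section 10, with the clinical team's confirmation. Leave the homicidal-ideation and self-harm triggers as they are.

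**Cost.** Amendment wording; sample size and treatment are unchanged. If the consent form promised destruction on withdrawal, an addendum is needed, and data from anyone who consented on that promise must be handled as promised unless they agree otherwise.
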